9.5 Analysis of secondary variables

9.5.1 Efficacy variables

The secondary variables of this study are change from baseline in daytime asthma symptoms, change from baseline in total daily SABA use, and change from baseline in AQLQ+12 over the 12 weeks of treatment. The local significance level for each secondary null hypothesis will be determined based on the closed testing procedure specified by [Figure 9-1](#). A range of

sensitivity analyses will be conducted on secondary endpoints under different missing data handling approaches in a similar fashion as those described in [Section 9.4.4](#).

9.5.1.1 Daytime asthma symptoms in patients

Daytime asthma symptoms are evaluated through four questions and each of them will be rated on a scale of 0 to 6. Higher scores indicate more severe asthma-related symptoms. A mean score will be calculated for the responses to 4 questions. The main analysis of the secondary endpoint of daytime symptoms will be performed for all patients over the entire age range (12 years and older). The baseline of daytime asthma symptoms will be defined as the average of the mean daytime asthma symptom score during the placebo run-in period. The mean of change from baseline in the daytime symptom scores over the 12 weeks of treatment will be analyzed using an analysis of covariance (ANCOVA) model in a similar fashion as the primary efficacy variable. The null hypothesis is that the treatment difference compared to placebo over the 12 weeks of treatment = 0, while the alternative hypothesis is that the treatment difference to placebo over the 12 weeks of treatment \neq 0. This model will be fitted to each of multiple imputations generated using a jump-to-reference approach as for the primary analysis.

The asthma diary included in this study to measure daytime asthma symptoms was validated in studies of patients aged 18 to 65 years ([Santanello et al 1997](#)). It was subsequently included as a measure in placebo-controlled studies of montelukast in patients aged 15 years and older ([Reiss et al. 1998](#) and [Malmstrom et al. 1999](#)) and shown to be responsive to both montelukast and inhaled beclomethasone therapy in this age range. Given the performance characteristics, particularly the responsiveness to asthma therapies, of the asthma diary are known for patients aged 15 years and older, a supportive analysis of the secondary endpoint of daytime symptoms will be included and be limited to patients aged 15 years and older.

9.5.1.2 Total daily use of SABA

Total daily use of SABA (the number of puffs taken in the previous 24 hours) by the patient will be analyzed using ePEF/ eDiary data. The baseline of SABA use will be defined as the average of total daily SABA use during the placebo run-in period. The mean of change from baseline in the total daily use of SABA over the 12 weeks of treatment will be analyzed using an ANCOVA model in a similar fashion as the primary efficacy variable. The null hypothesis is that the treatment difference compared to placebo over the 12 weeks of treatment = 0, while the alternative hypothesis is that the treatment difference to placebo over the 12 weeks of treatment \neq 0. This model will be fitted to each of multiple imputations generated using a jump-to-reference approach as for the primary analysis.

9.5.1.3 AQLQ+12

The change from baseline in AQLQ+12 at week 12 will be analyzed using an ANCOVA model in a similar fashion as the primary efficacy variable. The baseline of AQLQ+12 is defined as the last assessment prior to the first dose of study drug. Missing data of AQLQ+12 overall score will be imputed a jump-to-reference approach as for the primary analysis.

9.5.1.4 **Summary statistics for the secondary variables**

Summaries of absolute values and change from baseline in the three secondary variables will be presented by visit and by treatment group. Figures will be produced to visually show the mean and the mean change from baseline by visit over study period for each treatment group.

9.5.2 **Safety variables**

All safety data will be summarized for the safety set.

9.5.2.1 **Adverse events**

Adverse events after informed consent including asthma exacerbations will be summarized and listed.

Adverse events starting on or after the time of the first intake of study drug will be classified as treatment-emergent adverse events. Any adverse events that started during the study after informed consent before the time of the first intake of study drug will be classified as a prior adverse events and not included in tabulations of treatment emergent adverse events.

The following treatment emergent adverse event summaries will be produced, overall by system organ class and preferred term, overall by system organ class, preferred term and maximum severity, suspected drug-related adverse events by system organ class and preferred term, serious adverse events by system organ class and preferred term, and adverse events leading to permanent discontinuation of study-drug by system organ class and preferred term.

The number and percentage of patients with the most frequent AEs will be summarized by treatment.

Selected adverse events of special interest may be summarized and analyzed as well.

9.5.2.2 **Vital signs**

Data of the vital signs (systolic blood pressure, diastolic blood pressure, and pulse rate) will be summarized by treatment and scheduled visit. The maximum and minimum systolic blood pressure, diastolic blood pressure, and pulse rate post-baseline (including values from post-baseline unscheduled and premature discontinuation visits) can also be summarized by treatment. Absolute body weight will be summarized by scheduled visit. The change from baseline to each scheduled post-baseline visit will be summarized by vital sign parameter, scheduled visit and treatment with standard descriptive statistics.

Notable values and notable changes from baseline in vital signs will be summarized.

9.5.2.3 **Electrocardiogram (ECG)**

The changes from baseline will be summarized by ECG parameter, schedule visit where baseline and post baseline values are both available.

The following quantitative variables will be summarized by treatment at each scheduled post-baseline visit: ventricular rate, QT interval, RR interval, PR interval, QRS duration, heart rate, and Fridericia's QTc. The maximum QTc (including values from post-baseline unscheduled and premature discontinuation visits) will also be summarized.

Notable values and notable changes from baseline in quantitative ECG variables will be summarized.

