All adverse events must be treated appropriately. Treatment may include one or more of the following:

- no action taken (e.g. further observation only)
- investigational treatment dosage increased/reduced
- investigational treatment interrupted/withdrawn
- concomitant medication or non-drug therapy given
- non-drug therapy given
- patient hospitalized/patient's hospitalization prolonged (see [Section 7.2](#) for definition of an SAE)
- its outcome (not recovered/not resolved; recovered/resolved; recovering/resolving, recovered/resolved with sequelae; fatal; or unknown)

Once an adverse event is detected, it must be followed until its resolution or until it is judged to be permanent, and assessment must be made at each visit (or more frequently, if necessary) of any changes in severity, the suspected relationship to the study drug, the interventions required to treat it, and the outcome.

Information about common side effects already known about the investigational drug can be found in the investigator brochure (IB). This information will be included in the patient informed consent and should be discussed with the patient during the study as needed. Any new information regarding the safety profile of the medicinal product that is identified between IB updates will be communicated as appropriate, for example, via an investigator notification (IN) or an Aggregate Safety Finding. New information might require an update to the informed consent and has then to be discussed with the patient.

The investigator must also instruct each patient to report any new adverse event (beyond the protocol observation period) that the patient, or the patient's personal physician, believes might reasonably be related to study treatment. This information must be recorded in the

investigator's source documents; however, if the AE meets the criteria of an SAE, it must be reported to Novartis.

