7.2.2 SAE reporting

To ensure patient safety, every SAE, regardless of causality, occurring after the patient has provided informed consent and until 30 days after the last study visit must be reported to Novartis safety within 24 hours of learning of its occurrence. Any SAEs experienced after the 30 day period after the last study visit should only be reported to Novartis safety if the investigator suspects a causal relationship to study treatment.

All follow-up information for the SAE including information on complications, progression of the initial SAE and recurrent episodes must be reported as follow-up to the original episode within 24 hours of the investigator receiving the follow-up information. An SAE occurring at a different time interval or otherwise considered completely unrelated to a previously reported one must be reported separately as a new event.

Information about all SAEs is collected and recorded on the Serious Adverse Event Report Form; all applicable sections of the form must be completed in order to provide a clinically thorough report. The investigator must assess the relationship of each SAE to *each specific component of study treatment, (if study treatment consists of several components)* complete the SAE Report Form in English, and submit the completed form within 24 hours to Novartis. Detailed instructions regarding the submission process and requirements for signature are to be found in the investigator folder provided to each site.

Follow-up information is submitted as instructed in the investigator folder. Each re-occurrence, complication, or progression of the original event must be reported as a follow-up to that event regardless of when it occurs. The follow-up information should describe whether the event has resolved or continues, if and how it was treated, whether the blind was broken or not, and whether the patient continued or withdrew from study participation.

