### **2.7.1 Adverse events (AEs)**

All adverse events, including asthma exacerbations, coded with MedDRA using the most actual version at the time of database lock, will be listed. Unless otherwise specified, summaries will include treatment-emergent adverse events (TEAEs) only. AEs starting on or after the time of the first intake of study drug and not later than 7 days (30 days in the case of a serious AE) after the last intake of study drug will be classified as a TEAE. For those patients who enter the safety study (CQAW039A2315) directly after Visit 299, AEs (including serious AEs) starting after Visit 299 will not be considered as TEAEs in this study as they will be reported in CQAW039A2315.

As a general rule of censoring, patients who either completed the study or discontinue treatment prematurely and without the event of interest will be censored at the minimum out of the dates of last medication intake + 30 days, final visit date, and date of death. The number and percentage of patients who reported TEAEs will be summarized by primary system organ class (SOC), preferred term (PT), and treatment group for

- all adverse events (AEs)
- all AEs by maximum severity
- AEs suspected to be related to study drug
- AEs by standardized MedDRA query (SMQ) level
- serious AEs (SAEs)
- AEs leading to permanent study drug discontinuation
- AEs of special interest

Unless otherwise specified, primary system organ classes will be sorted alphabetically and, within each primary system organ class, the preferred terms will be sorted in descending order of frequency in the QAW039 150 mg once daily treatment group. If a patient reported more than one AE with the same preferred term, the AE will be counted only once. If a patient reported more than one AE within the same primary system organ class, the patient will be counted only once at the system organ class level.

In addition, the most frequent AEs will be presented by preferred term in descending order of frequency in the QAW039 150 mg once daily treatment group.

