### **2.7.2 Deaths**

The number of deaths resulting from TEAEs will be summarized by SOC and PT. All the deaths in the clinical database including those occurring during screening will be listed.

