#### 4 Change to protocol specified analyses

- Section 9.2 in the study protocol states that the age of the patient will be calculated from the date of birth to date of Visit 1. However, since date of birth is not captured on the CRF page and age (in years) at the time of informed consent is entered into CRF, there is no need to re-calculate age.
- Shift tables relative to the normal reference ranges to summarize the on-treatment change from baseline to post-baseline for each laboratory parameter or ECG parameter or vital sign assessments will not be presented.
- Study protocol defines treatment emergent adverse events as those events starting on or after the time of the first intake of study drug and until the day after the last intake of study drug. However, in order to maintain consistency with the submission documents, for analysis purposes the following updated definitions are considered:  
AEs starting on or after the time of the first intake of study drug and not later than 7 days (30 days in the case of a serious AE) after the last intake of study drug will be classified as a TEAE.
- Added the responder analysis for AQLQ improvement
- Added more details to liver function tests including eDISH plot
- Added analysis for renal events and liver events according to project level alignment
- The following analyses, though pre-specified in the protocol, may not be critical for decision making purposes and hence will be reported outside of CSR:

█ [REDACTED]

- In protocol 9.4.4, supportive analysis for the primary endpoint based on other missing data imputation approaches: pattern mixture approach combining the jump to reference and missing at random approaches by distinguishing reasons for discontinuation of treatment and retrieved dropout imputation approach.
- In protocol Section 9.4.4, subgroup analyses for BMI, number of exacerbations in the previous year, ACQ tertiles, [REDACTED].
- Summaries on post-treatment discontinuation events to be produced for adverse events and serious adverse events by system organ class and preferred term.

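### Treatment-emergent AEs are defined by start date alone, so an event that began before the first double-blind dose and worsens on treatment can be missing from the by-arm TEAE tables

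*Protocol*

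**What the plan says.** Protocol 9.5.2.1 gives the inclusion rule: "Adverse events starting on or after the time of the first intake of study drug will be classified as treatment-emergent adverse events". It then disposes of whatever began earlier but after consent: such events, starting "before the time of the first intake of study drug will be classified as a prior adverse events and not included in tabulations" of TEAEs. No exception is made for what the event does later.

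SAP 2.7.1 keeps the same anchor and adds an end to the window: "AEs starting on or after the time of the first intake of study drug and not later than 7 days" after the last intake, or 30 days for a serious event. SAP Section 4 records this as a departure from the protocol, introduced with "However, in order to maintain consistency with the submission documents, for analysis purposes the following updated definitions are considered". The change concerns the end of the window and leaves classification by start date as it was.

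The definition controls nearly all AE output. SAP 2.7.1 says: "Unless otherwise specified, summaries will include treatment-emergent adverse events (TEAEs) only". The tables it then names cover all AEs, maximum severity, suspected relationship, standardized MedDRA queries, serious events, events leading to permanent discontinuation and events of special interest. SAP 2.7.2 applies the same restriction to deaths: "The number of deaths resulting from TEAEs will be summarized by SOC and PT".

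On recording, Protocol 7.1 says: "Once an adverse event is detected, it must be followed until its resolution or until it is judged to be permanent", with severity reassessed at each visit. For serious events Protocol 7.2.2 says: "Each re-occurrence, complication, or progression of the original event must be reported as a follow-up to that event regardless of when it occurs".

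**The concern.** A definition that looks only at onset separates events by when they began, not by whether they got worse on drug. A mild complaint that starts in the run-in and becomes severe or serious after randomization is the kind of event a safety comparison should count, yet under this rule it is a prior event. The protocol states the exclusion outright, so this is more than an unstated detail.

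Safety is the fourth secondary objective. Protocol 3.6 names palpitations, headache, diarrhea, nausea, nasopharyngitis and dizziness among the possible side effects of QAW039. These are common complaints that can already be present at the first dose. If the drug aggravates them, the lost cases fall more often in the QAW039 arm, and the TEAE comparison moves toward no difference.

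**Working it through.** The documents give no figure to reproduce, so the check sets the rules side by side, traces one case through them, and then uses the documents' own timings.

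**1. Which rules allow for worsening.**

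| Rule | Counts new onset on treatment | Counts worsening of what was there before |
|---|---|---|
| Protocol 9.5.2.1, AEs | Yes | No; expressly prior |
| SAP 2.7.1, AEs | Yes, to 7 or 30 days after last intake | No clause |
| SAP 2.7.2, deaths summary | Follows the TEAE rule | No clause |
| Protocol 7.2.1, SAE definition | Yes | Yes, but assigns no start date |
| SAP 2.7.3.3, notable laboratory values | Yes | Named, but requires a baseline that is not notable |
| SAP 2.7.3.3, liver function tests | Yes | Yes, including when the criteria were met at baseline |

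**2. One hypothetical case.** A headache starts on Day -5 as mild and becomes severe on Day 20.
- Kept as one record: its start, Day -5, precedes Day 1. It is a prior event and enters no TEAE table.
- Entered as a second record on worsening: its start, Day 20, is after Day 1 and within the window. It is a TEAE and is counted as severe.

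The result therefore depends entirely on how the site records the change.

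**3. What the documents say about recording.** Protocol 7.1 asks for one duration per event, with a start and an end date, and for follow-up of severity. It does not say whether a change of severity opens a new record. Protocol 7.2.2 concerns progression of events already reported as serious. SAP 2.7.1.2, on registry tables, merges consecutive records with the same system organ class and preferred term when the gap is at most one day, whatever their severity or seriousness. That implies such records can exist, but it is a counting rule and instructs no site. Splitting is thus possible but nowhere required.

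**4. Where an unsplit case still shows.** All AEs are listed (SAP 2.7.1) and all deaths are listed (SAP 2.7.2). Reasons for stopping study treatment are shown under SAP 2.4.1.1 without restriction to TEAEs, though not by preferred term.

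**5. Which events are exposed.** The interval runs from consent to the first double-blind dose. Protocol 3.1 allows consent up to 14 days before Visit 1, then up to 2 weeks of screening and 1 week of run-in:
- Longest: 14 + 14 + 7 = 35 days; 35/84 = 42% of the 84 treatment days.
- Consent at Visit 1 with full-length screening: 14 + 7 = 21 days; 21/84 = 25%.
- If the protocol's first intake is read as the first run-in placebo tablet, which its glossary and Section 5.5.4 also call study drug: 35 − 7 = 28 days at most.

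A condition present before consent is medical history. If it worsens on treatment it can be entered as a new AE, so it is not caught by this rule.

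**6. How many patients.** This cannot be computed: the documents give no rate of AEs ongoing at the first dose or of their worsening. For scale only, assume that 10% to 20% of an arm of 325 have such an AE and that 2% to 10% of those worsen:
- Low: 325 × 0.10 × 0.02 = 0.65 patients per arm.
- High: 325 × 0.20 × 0.10 = 6.5 patients per arm.

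Both percentages are assumptions without a source in the documents, and the verdict does not rest on them.

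**The case against.** The strongest reply is that the loss is not established. It requires the worsened event to remain one record with its pre-dose start date, and no section says that it does. The registry counting rule in SAP 2.7.1.2 fits a practice of splitting records, under which the start-date rule already works. This stands as far as it goes: a reader might infer that these events are certain to be left out of every TEAE table, and the documents do not support that. They do support the conditional statement, because no section requires splitting.

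A reader might also take Protocol 7.2.2 as proof that a worsened event keeps its early date. It shows this at most for events that were already serious before dosing. A non-serious run-in event that turns serious on drug has no earlier SAE report to follow up.

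Nor is the AE rule the only one that neglects worsening. Read literally, the general laboratory rule also leaves out a value that was notable at baseline and then deteriorates.

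There are partial safeguards. Besides the listings and discontinuation reasons, SAP 2.7.1.2 counts deaths from serious AEs without expressly limiting them to TEAEs, and the Data Monitoring Committee reviews safety data with unblinded access. It would therefore be wrong to infer that an excess could not be seen between arms at all. What these sources lack is a by-arm rate by preferred term, severity, seriousness and relationship.

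Finally, eligibility removes many candidates. An exacerbation in screening or run-in is a failure (Protocol 6.4.3), and a patient with a respiratory infection or asthma worsening in screening is to be re-screened (exclusion criterion 13). This lowers the number further but leaves complaints such as headache or palpitations untouched.

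**Conclusion.** The point holds in conditional form. The TEAE definition looks at onset only, and the protocol expressly sets aside events that began between consent and first intake. Unless sites open a new record on worsening, which neither document instructs, an event that becomes more severe, serious or fatal on double-blind treatment is missing from the by-arm TEAE tables of severity, seriousness and relatedness, from the table of AEs leading to discontinuation if it stops treatment, and from the TEAE deaths summary.

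The number of patients is probably small and cannot be derived from the documents; the illustrative range above should not be read as an estimate. The rule applies equally to both arms. It distorts the comparison only if QAW039 aggravates existing events, and then by hiding an excess. The effect would matter most in tables with few events, such as serious AEs and deaths. No efficacy analysis is affected.

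**What to change.** In SAP 2.7.1 and Protocol 9.5.2.1, define a TEAE as an AE that starts on or after the first double-blind dose, or that started earlier and increases in severity or becomes serious (including fatal) on or after that dose. Keep the SAP's 7-day limit, its 30-day limit for serious events, and its handling of patients who enter the safety study. Naming the double-blind dose also removes the ambiguity over run-in placebo.

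State in the CRF completion guideline that such worsening is entered as a new AE record with its own start date. This one mechanism supplies the date the definition needs: the new record is treatment-emergent and the earlier one stays prior. Double counting is limited because SAP 2.7.1 already counts a preferred term once per patient. The SAE follow-up rule in Protocol 7.2.2 can stay unchanged.

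An event that leads to stopping treatment without becoming more severe or serious would remain prior under this wording, and would show in the discontinuation reasons and listings.

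The cost is slightly higher TEAE counts in both arms, a sentence in each document and a line in the guideline. The protocol sentence needs an amendment under Protocol 11.1. SAP Section 4, which already records one change to the TEAE definition, is the place to note this one.
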